**Table 1-1: Schedule of activities**

Study Period	Screening Period (28 days)															SFU Or Withdrawal Visit (maximum of 8 days after the last dose) a
		Single-dose Period				Multiple-dose Period										
12-lead ECG d	X		X	X			X	X	X	X	X	X	X	X	X	X
PSL administration			X e				X f	X g	X g	X g	X h	X i	X i			
PK blood sampling			X j	X j	X j						X k					
PK urine sampling			X l	X l	X l	X l	X l				X m					
Adverse events	X	X	X	X	X	X	X	X	X	X	X	X	X	X	X	X
Stay in study center		X	X	X	X	X	X	X	X	X	X	X	X	X		

BP=blood pressure; C-SSRS=Columbia-Suicide Severity Rating Scale; CYP2C19=cytochrome P450 family 2 subfamily C; ECG=electrocardiogram;

HBV=hepatitis B virus; HCV=hepatitis C virus; HIV=human immunodeficiency virus; PK=pharmacokinetic; PSL=padsevonil; SFU=Safety Follow-up Visit

a The Safety Follow-up Visit will be performed 7 days ( $\pm 1$  day) after the last administration of PSL. Idem for the Withdrawal Visit, if applicable.

b A complete physical examination will be conducted at Screening and SFU. A brief physical examination will be conducted at all other visits, including at discharge.

c On dosing days, vital signs will be performed predose and 3 hours postdose. Blood pressure measurements will be performed in both supine and standing positions for orthostatic measurement at Screening (supine BP after the study participant has been lying down for 5 minutes and then standing BP after 1 minute and 3 minutes) and in a supine position for routine BP measurements at all assessments.

d 12-lead ECG will be performed after a rest of  $\geq 5$  minutes at Screening and at predose, 24 hours postdose, and at the SFU Visit. All ECG recordings will be performed in triplicate but no more than 2 to 3 minutes apart. The full set of triplicates should be completed in less than 9 minutes.

e PSL 200mg will be administered in the morning on Day 1 during the Single-dose Period.

f PSL 100mg will be administered in the morning and evening on Day 6 during the Multiple-dose Period.

g PSL 200mg will be administered in the morning and evening from Day 7 to Day 9 during the Multiple-dose Period.

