#### **8.4.1 Physical examination**

Physical examinations will be performed at Screening and at the time points specified in Section 1.3.

A complete physical examination will include, at a minimum, general appearance; ear, nose, and throat; eyes, hair, and skin; and assessments of the Cardiovascular, Respiratory, Gastrointestinal, Neurological, Musculoskeletal, and Hepatic systems. Height and weight will also be measured and recorded.

A brief physical examination will include, at a minimum, assessments of the skin, lungs, cardiovascular system, and abdomen (liver and spleen).

Investigators should pay special attention to clinical signs related to previous serious illnesses.

Clinically relevant findings or worsening of previous findings will be recorded as AEs.

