**Table 2-1: Schedule of activities**

Study Period	Screening Period (28 days)															SFU Or Withdrawal Visit (maximum of 8 days after the last dose) a	
		Single-dose Period							Multiple-dose Period								
Study Day	-29 to -2	-1	1	2	3	4	5	6	7	8	9	10	11	12	13	14	
Informed consent	X																
Inclusion/exclusion	X		X														
Body weight and height	X																
CYP2C19 genotyping	X																
Exploratory genotyping			X n														
Demographics, habits, lifestyle	X																
Medical/surgical history	X																
Concomitant medication/medical procedures	X	X	X	X	X	X	X	X	X	X	X	X	X	X	X	X	
Physical examination b	X	X														X	
Psychiatric and mental status	X	X	X	X	X	X	X	X	X	X	X	X	X	X	X	X	
C-SSRS	X	X								X				X		X	
Drug screen, ethanol breath test	X	X															
Serology (HBV, HCV, HIV, syphilis)	X																
Clinical laboratory tests	X	X					X							X		X	
Vital signs c	X	X	X	X	X	X	X	X	X	X	X	X	X	X	X	X	

Study Period	Screening Period (28 days)																	SFU Or Withdrawal Visit (maximum of 8 days after the last dose) a
		Single-dose Period					Multiple-dose Period											
12-lead ECG d	X		X	X			X	X	X	X	X	X	X	X	X	X	X	
PSL administration		X e					X f	X g	X g	X g	X h	X i	X i					
PK blood sampling		X j	X j	X j								X k						
PK urine sampling		X l	X l	X l	X l	X l						X m						
Adverse events	X	X	X	X	X	X	X	X	X	X	X	X	X	X	X	X	X	
Stay in study center		X	X	X	X	X	X	X	X	X	X	X	X	X	X	X		

BP=blood pressure; C-SSRS=Columbia-Suicide Severity Rating Scale; CYP2C19=cytochrome P450 family 2 subfamily C; ECG=electrocardiogram; HBV=hepatitis B virus; HCV=hepatitis C virus; HIV=human immunodeficiency virus; PK=pharmacokinetic; PSL=padsevonil; SFU=Safety Follow-up Visit

a The Safety Follow-up Visit will be performed 7 days ( $\pm 1$  day) after the last administration of PSL. Idem for the Withdrawal Visit, if applicable.

b A complete physical examination will be conducted at Screening and SFU. A brief physical examination will be conducted at all other visits, including at discharge.

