### **3.2.2 Study periods**

For each participant completing the study, the expected maximum duration of participation will be approximately 49 days with a maximum of 8 days exposure to PSL, and will consist of the following periods:

- Screening Period: Day -29 to Day -2
- Single-dose Period: Day -1 to Day 5
- Multiple-dose Period: Day 6 to Day 14
- SFU or Withdrawal Visit (maximum of 8 days after the last dose)

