### **3.3 Definition of Baseline values**

In general, Baseline will be the last non-missing assessment prior to dosing. The definition for each measurement is described below:

- Hematology, serum chemistry, urinalysis: Baseline is defined as Day -1. If Day -1 value is missing the Screening value will be used.
- Vital Signs: Baseline is defined as predose on Day 1. If predose on Day 1 is missing or multiple assessments occur, the last measure prior to dosing will be used.
- ECG: The mean of the last three measurements predose on Day 1 will be taken as Baseline. If there are less than three replicates at Day 1 predose, the mean of the available replicates (predose) will be taken as baseline.

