## 6.1 Demographics

All demographic characteristics obtained during the Screening Period will be summarized by genotype group and overall for the SS. This summary will include age (in years), sex (male), weight (kg), height (cm), body mass index (BMI in kg/m^2), race (Asian), ethnicity (Not Hispanic or Latino), ethnic subgroup (Japan) and CYP2C19 genotype.

The summary of age will include descriptive statistics and categorical summaries, the latter based on requirements for clinicaltrials.gov reporting ( $\leq 18$ , 19 to  $< 65$ , and  $\geq 65$  years) and the European Union Drug Regulating Authorities Clinical Trials (EudraCT) reporting ( $< 18$ , 18 to  $< 65$ , 65 to  $< 85$ , and  $\geq 85$  years).

A by-participant listing of demographic characteristics as well as the date of birth will be presented for the ES.

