## 9.3 Derivations of pharmacokinetic parameters

- AUC will be calculated as  $AUC = AUC_{(0-t)} + C_{last}/\lambda_z$ , where  $C_{last}$  is the last quantifiable plasma concentration and  $\lambda_z$  is the apparent terminal elimination rate constant.
- $AUC_{(0-t)}$  will be calculated using the linear-up log-down trapezoidal rule. If single data points for plasma concentrations are missing, the parameter will be derived by interpolating with regard to the 2 neighboring non-missing concentrations.
- $t_{1/2}$  will be calculated as  $\ln 2/\lambda_z$  where a simple linear regression (slope =  $-\lambda_z$ ) of natural log ( $\ln$ ) concentration vs time for data points in the terminal phase of the concentration-time curve.
- Metabolite to parent ratio ( $m/p$ ) based on  $C_{max}$  will be calculated using  $C_{max}$  of metabolite divided by  $C_{max}$  of parent (PSL) and  $C_{max,ss}$  of metabolite divided by  $C_{max,ss}$  of parent for single and multiple dose respectively.
- Metabolite to parent ratio ( $m/p$ ) based on  $AUC$  will be calculated using  $AUC$  of metabolite divided by  $AUC$  of parent and  $AUC_{\tau}$  of metabolite divided by  $AUC_{\tau}$  of parent for single and multiple dose respectively.
- Body weight (BW) normalized parameters (ie,  $C_{max,bw}$ ,  $AUC_{(0-t),bw}$ ,  $AUC_{,bw}$ ,  $C_{max,ss,bw}$ , and  $AUC_{\tau,bw}$ ) will be calculated using the following formula where BW is measured on Day -1:

$$\text{Parameter}_{bw} = \text{Parameter} \times \frac{BW}{70}$$

- $CL_r$  will be calculated as  $A_e/AUC$  and  $A_e/AUC_\tau$  for single and multiple dosing respectively.
- $f_e$  will be calculated as  $A_e/\text{Dose}$  for PSL and as  $(A_e \text{ of metabolite}/\text{Dose}) \times (\text{molecular weight (MW) parent}/\text{MW metabolite})$  where the MW of PSL is 432.8, the MW of metabolite [REDACTED] is 419, the MW of metabolite [REDACTED].
- $CL_{form}$  will be calculated as  $(A_e \text{ of metabolite}/\text{AUC of parent}) \times (\text{MW parent}/\text{MW metabolite})$  for single-dose period and as  $(A_e \text{ of metabolite}/\text{AUC}_\tau \text{ of parent}) \times (\text{MW parent}/\text{MW metabolite})$  for multiple-dose period.
- Accumulation ratio of  $C_{max}$  ( $RC_{max}$ ) will be calculated using  $C_{max,ss}$  following multiple dosing divided by  $C_{max}$  following a single dose for PSL and its metabolites.

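### Does the Day -1 weight named in SAP 9.3 leave the five body-weight-normalized PK parameters without a planned input?

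*SAP*

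**What the plan says.** SAP 9.3 gives one formula for the normalized parameters, Parameter × BW/70, and states that they "will be calculated using the following formula where BW is measured on Day -1". The five are listed among the other, non-primary PK endpoints (SAP 2.1 and 9; protocol Table 3-1). All five enter the genotype ANOVA of SAP 9.2, for padsevonil and its metabolites.

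The collection side reads differently. In protocol Table 1-1 and SAP Table 2-1 the row "Body weight and height" has a single mark, in the Screening column. SAP 3.2.2 sets the window: "Screening Period: Day -29 to Day -2". Day -1 belongs to the Single-dose Period.

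A physical examination is scheduled on Day -1, but footnote b of the schedule says: "A complete physical examination will be conducted at Screening and SFU. A brief physical examination will be conducted at all other visits". Protocol 8.4.1 attaches weight to the complete examination ("Height and weight will also be measured and recorded"). For the other type it says: "A brief physical examination will include, at a minimum, assessments of the skin, lungs, cardiovascular system, and abdomen (liver and spleen").

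**The concern.** A derivation rule should name a quantity that the study collects. SAP 9.3 names a specific day, and nothing in either schedule produces a weight on that day. The Day -1 examination does not fill the gap, because it is the brief one and its listed content omits weight.

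SAP 3.3 also looks unhelpful on first reading. For laboratory values it gives an explicit fallback ("If Day -1 value is missing the Screening value will be used"), but it has no entry for weight.

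If the gap were real in practice, five parameters per analyte could not be derived as written. Two programmers might use different weights, or a substitution might go unrecorded. SAP 1 requires an SAP amendment when an analysis definition has to be modified before database lock, so an undocumented substitution would be a traceability fault.

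**Working it through.** **Step 1. Which weights could be used?**

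| Occasion | Weight planned? | Source |
|---|---|---|
| Screening, Day -29 to Day -2 | Yes | Both schedules; complete examination (protocol 8.4.1) |
| Day -1 | No | No mark in either schedule; brief examination |
| Safety Follow-up | Through the complete examination only, after dosing | Footnote b; protocol 8.4.1 |

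Only the Screening weight is both planned and predose. It should exist for everyone dosed, because inclusion criterion 4 sets a minimum of 50 kg and a BMI range. SAP 6.1 already uses it: "All demographic characteristics obtained during the Screening Period will be summarized by genotype group and overall for the SS", and weight is in that list.

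**Step 2. Do other rules point to it?** SAP 3.3 opens with a general definition of Baseline as the last available predose assessment. Protocol 9.2 has the same default. SAP 4.2 and protocol 9.7 add that the last predose value stands in for a missing Baseline value. SAP 9.3 does not label BW a Baseline value, so these rules do not settle the point formally. They do all lead to the Screening weight, and no rule leads elsewhere.

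**Step 3. How far could the choice of day move a result?** The formula is linear in BW, so an x% difference in weight changes that participant's value by x%. A percentage shift common to all groups cancels in a ratio of geometric means.

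The documents give no figure for weight change between Screening and Day -1, which are 1 to 28 days apart. Assume 1 to 2 kg:

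- at an assumed 65 kg: 1/65 = 1.5%, 2/65 = 3.1%
- at the 50 kg minimum: 1/50 = 2%, 2/50 = 4%

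*As random error.* The planning CV of 39% (protocol 9.9) is for un-normalized AUCtau and is used here as a stand-in.

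- Log variance: ln(1 + 0.39²) = 0.1416
- Half-width of the 90% CI: t(0.95, df) × √(2 × 0.1416/n)
- n = 13 per group, df = 36: half-width 0.2492; upper limit at ratio 1.3 is 1.3 × exp(0.2492) = 1.668
- n = 11 per group, df = 30: half-width 0.2723; upper limit 1.3 × exp(0.2723) = 1.707

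Adding the weight-error variance to 0.1416:

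| Error SD | Added variance | Share of 0.1416 | Half-width multiplier | Upper limit, n = 13 | Upper limit, n = 11 |
|---|---|---|---|---|---|
| 1.5% | 0.000225 | 0.16% | 1.0008 | 1.6682 | 1.7073 |
| 3% | 0.0009 | 0.64% | 1.0032 | 1.6692 | 1.7084 |
| 4% | 0.0016 | 1.13% | 1.0056 | 1.6702 | 1.7095 |

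*As a shift between groups.* Suppose, as an extreme, that every participant in one genotype group changed by 4% and nobody in the other did. The upper limit would become 1.668 × 1.04 = 1.735 with 13 per group, or 1.707 × 1.04 = 1.775 with 11. Both remain below 2.0. Nothing in the plan suggests that predose weight change would differ by CYP2C19 genotype.

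**The case for a change.** The strongest case for a change is that SAP 9.3 is specific where the Baseline rules are general. It names a day and does not call BW a Baseline value. SAP 3.3 spells out a Day -1-to-Screening fallback for laboratory data and is silent on weight. The SAP says that it supplies all the information needed for the analysis, and one clause would bring it into line with both schedules at no cost in data.

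The textual part of this stands: the clause and the schedules disagree, and a broken table is an unlikely explanation because the weight row has the same single-mark pattern in both documents. The consequence does not follow. Applying an existing general rule when the named value was not collected is arguably not the modification of a definition for which SAP 1 requires an amendment. If a site did weigh participants on Day -1, which the minimum content of the brief examination permits, the clause works as written. If not, the Screening weight is the only scheduled predose value. Protocol 9 already requires departures from the final SAP to be documented in the clinical study report, which covers traceability.

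SAP Amendment 1 revised another item in 9.3 and left this clause alone. That says nothing about which weight was used.

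**Conclusion.** The mismatch is real but clerical, and correcting it would bring no gain. The weight that a correction would name is the weight an analyst would use anyway. It touches five non-primary parameters per analyte. The primary parameters and the sample-size basis do not depend on weight.

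Under the assumed 1 to 2 kg difference, the upper 90% limit moves by about 0.002 (1.668 to at most 1.670 with 13 per group), against 2.0. This rests on three assumptions: the size of the weight change, which the documents do not give; the 39% CV of un-normalized AUCtau standing in for the normalized parameters; and the difference behaving as random error unrelated to genotype. Even the one-sided 4% shift leaves the limit below 2.0 at a ratio of 1.3. No result or conclusion is expected to change.

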## 10 SAFETY ANALYSES

Safety analyses will be carried out in the SS unless otherwise stated. In listings, data will be presented by participant number and time point within each genotype group.

### 10.1 Extent of exposure

All study medication administration details will be listed by treatment period and participant. The listing will include the date and time of administration of the morning and evening dose, depending on the treatment period.

### 10.2 Adverse events

All Adverse events (AEs) will be coded using the MedDRA® and characterized as pretreatment and treatment emergent according to the intake of the study medication. AEs with a start date prior to the first dose of study medication will be defined as pretreatment AEs. A treatment emergent AE (TEAE) is defined as any AEs with a start date/time on or after the first dose of study medication or any unresolved event already present before administration of study medication that worsens in intensity following exposure to the treatment. Where dates are missing or partially missing, AEs will be assumed to be treatment emergent, unless there is clear evidence to suggest that the AE started prior to the first dose of study medication. Missing or partially missing dates for AEs will be handled as described in Section 4.2.4.

AEs will be attributed to the treatment period in which they start. Thus, all AEs starting after the first intake of PSL through Day 5 will be attributed to Single-Dose Period; all AEs starting after PSL intake on Day 6 will be attributed to the Multiple-Dose Period and AEs starting more than 168 hours post last dose of PSL will be attributed to the SFU period.

All AEs will be recorded in the Case Report form (CRF) from the time of informed consent until study completion or termination. All AEs will be coded (see Section 3.8) and categorized by intensity (mild/moderate/severe) and relationship (related/not related) to study drug PSL as judged by the Investigator.

The number and percentage of participants who experience TEAEs will be summarized by MedDRA SOC, PT, treatment period, genotype and by characterization according to the intake of PSL.

The occurrence and incidence of TEAEs will also be summarized by intensity and relationship to PSL. TEAEs leading to discontinuation and serious TEAEs will also be summarized by treatment group and by characterization according to the intake of PSL.

Summaries of TEAEs will include the following:

- Incidence of TEAEs (overview including number and percentage of participants with any TEAEs, serious TEAEs, discontinuations due to TEAEs, drug-related TEAEs, severe TEAEs and TEAEs leading to death; event counts will also be included)
- Incidence of TEAEs
- Incidence of serious TEAEs
- Incidence of TEAEs by relationship
- Incidence of TEAEs by intensity
- Incidence of TEAEs by maximum relationship
- Incidence of TEAEs by maximum intensity
- Incidence of TEAEs leading to discontinuation by relationship
- Incidence of fatal TEAEs by relationship
- Incidence of serious TEAEs by relationship
- Incidence of non-serious TEAEs above reporting threshold of 5% of participants

Summary tables will contain counts of study participant, percentages of study participants in parentheses and the number of events where applicable. A participant who has multiple events in the same SOC or PT will be counted only once in the participant counts but all events will be included.

In summaries including relationship, the following relationships will be summarized: 'Not related', 'Related'. Participants who experience the same event multiple times will be included in the most related category for tabulations by maximum relationship. Events with missing relationship will be considered as 'Related' but recorded as missing in the listings.

In summaries including intensity, the following intensity categories will be summarized: 'Mild', 'Moderate', 'Severe'. Participants who experience the same event multiple times will be included in the most severe category for tabulations by maximum intensity. Events with missing intensity will be considered as 'Severe' events for summary purposes but recorded as missing in the listings.

Adverse event summaries will be ordered alphabetically by SOC and decreasing frequency of PT within SOC.

A listing for all AEs will be presented by participant, treatment period and will include the onset date/time and outcome date/time of the event (including relative days), the AE duration (derived), time to onset (derived), pattern of event, intensity, relationship, action taken and outcome. In addition, the listing will flag AEs that led to discontinuation, TEAEs and SAEs.

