### **2.3 Benefit/risk assessment**

Overall, the clinical pharmacology and clinical studies in drug-resistant epilepsy demonstrated the adverse event (AE) profile of PSL is generally consistent with the pharmacological activity of the product, and as expected in the context of early dose escalation studies in healthy study participants and patients with epilepsy. The safety findings to date suggest that the AEs experienced by study participants receiving single and repeated doses of PSL are limited principally to central nervous system effects. The AEs tend to be dose related in frequency and intensity, self-limiting, and tend to decrease in intensity over the first few days of dosing.

Reported acute psychiatric serious adverse events (SAEs) are consistent with AEs of other AEDs, including SV2A ligands. Events were transient, acute, and required admission to

psychiatric care and medical treatment. The events in healthy study participants (n=2) occurred early after initiation or cessation of PSL which was done without titration or tapering. The psychotic effect in an epilepsy study participant (EP0069) emerged after dramatic improvement in seizure control and electroencephalogram activity a few weeks after the start of PSL, suggesting a “forced normalization” (Clemens, 2005, Loganathan et al, 2015). Dose reduction of PSL and medical treatment resulted in complete resolution of psychosis within days, as the treatment with PSL continued. The occurrence of acute psychiatric SAEs in these three study participants administered PSL highlights the need to consider the possibility of significant psychiatric AEs and to maintain vigilance for such effects. The mitigation plan for acute psychiatric SAEs involves gradual titration and taper, which are known to improve tolerability of AEDs and monitoring for psychiatric and mental status changes.

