##### **8.5.1 Time period and frequency for collecting adverse events and serious adverse events information**

All AEs and SAEs will be collected from the signing of the ICF and at the time points specified in the Schedule of activities (Section 1.3).

Medical occurrences that begin before the start of study medication but after obtaining informed consent will be recorded on the Medical History/Current Medical Conditions section of the eCRF and not the AE section.

All SAEs will be recorded and reported to the Sponsor or designee within 24 hours, as indicated in Appendix 3 (Section 10.3). The Investigator will submit any updated SAE data to the Sponsor within 24 hours of it being available.

The Investigator is specifically requested to collect and report to UCB (or its representative) any SAEs (even if the Investigator is certain that they are in no way associated with the study medication), up to 30 days from the end of the study for each study participant, and to also inform study participants of the need to inform the Investigator of any SAE within this period. Serious AEs that the Investigator thinks may be associated with the study medication must be reported to UCB regardless of the time between the event and the end of the study.

The method of recording, evaluating, and assessing causality of AE and SAE and the procedures for completing and transmitting SAE reports are provided in Appendix 3 (Section 10.3).

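### SAP 10.2 keeps adverse events in the Multiple-Dose Period until 168 hours after the last dose, so period-level TEAE summaries mix on-treatment and post-treatment events and the SFU period can hold almost no non-serious events

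*SAP*

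**What the plan says.** SAP 10.2 attributes each AE to the period in which it starts. After the Single-Dose Period, which runs through Day 5, "all AEs starting after PSL intake on Day 6 will be attributed to the Multiple-Dose Period". The follow-up period then opens a week after dosing has ended: "AEs starting more than 168 hours post last dose of PSL will be attributed to the SFU period". A TEAE includes "any AEs with a start date/time on or after the first dose of study medication", with no upper time limit. On collection, "All AEs will be recorded in the Case Report form (CRF) from the time of informed consent until study completion or termination". SAP 5.1 and Protocol 4.4 tie completion to the last procedure in the schedule of activities, which is the SFU visit.

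Other sections draw the periods differently:

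- SAP 3.2.2 gives "Multiple-dose Period: Day 6 to Day 14" and then, as the next entry, "SFU or Withdrawal Visit (maximum of 8 days after the last dose".
- SAP 3.6 lists two periods for summaries, Single-dose and Multiple-dose, and no SFU period.
- SAP 6.4.2 places concomitant medications taken during follow-up in the Multiple-Dose Period.

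The schedule of activities puts the last dose in the evening of Day 12 and the SFU visit 7 (±1) days later. Participants leave the center on the morning of Day 14. Protocol 8.5.1 extends collection for SAEs only, "up to 30 days from the end of the study for each study participant".

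**The concern.** The cut-off that opens the SFU period for AEs coincides with the nominal time of the visit at which routine AE collection stops. A non-serious event can therefore hardly ever be attributed to follow-up. Events that start after dosing has ended, including those in the days after discharge, are counted with events that start on treatment. An event on Day 16 is a Multiple-dose event under SAP 10.2 but lies outside that period under SAP 3.2.2.

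This matters for interpretation. Incidence of TEAEs is the secondary endpoint (SAP 2.1), and SAP 10.2 tabulates it by treatment period. Protocol 2.3 reports that acute psychiatric SAEs in two healthy participants "occurred early after initiation or cessation of PSL which was done without titration or tapering", and it names gradual titration and taper as mitigation. Whether events follow the end of this study's taper is a question that a safety reader will bring to the tables, and the period summaries as specified do not answer it.

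**Working it through.** **Inputs.** Last dose: Day 12 evening (schedule of activities). SFU visit: 6, 7 or 8 days later, so Day 18, 19 or 20. SFU period for AEs: opens 168 h after the last dose (SAP 10.2). Multiple-dose Period: Day 6 to Day 14 (SAP 3.2.2).

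**1. Reproduce the plan's calendar.** Day -1 plus Days 1 to 20 gives 1 + 20 = 21 days on study, and 28 + 21 = 49 days, as stated. The Multiple-dose Period is 14 − 6 + 1 = 9 days, also as stated.

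**2. Cut-off against visit, in whole days.** 168 / 24 = 7 days. Visits at 6, 7 and 8 days are at 144, 168 and 192 h. Subtracting 168 h leaves −24, 0 and +24 h.

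**3. With clock times.** The documents give none, so I assume an evening dose between 18:00 and 23:00 and a visit between 08:00 and 17:00. Hours from dose to visit = (visit day − 12) × 24 + visit hour − dose hour. SFU time = max(0, that value − 168).

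| Visit day | Dose to visit (h) | SFU-period time (h) |
|---|---|---|
| 18 | 129 to 143 | 0 |
| 19 | 153 to 167 | 0 |
| 20 | 177 to 191 | 9 to 23 |

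If the three visit days were equally likely (an assumption), the mean would be 9/3 = 3 h to 23/3 = 7.7 h per participant.

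**4. Length of the Multiple-dose AE window.** Take the first Day 6 dose at 08:00 and the last dose at 20:00 on Day 12 (both assumed). Dosing spans 6 × 24 + 12 = 156 h, or 6.5 days. Adding 168 h gives 324 h = 13.5 days, of which 7 / 13.5 = 52% follows the last dose. Routine collection stops at the visit, so with a 09:00 visit the observed share is 133 / (156 + 133) = 46% for Day 18, 157 / (156 + 157) = 50% for Day 19, and 168 / 324 = 52% for Day 20.

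**5. Outpatient part.** From discharge on Day 14 (09:00 assumed) to the 168 h mark at 20:00 on Day 19 is 5 × 24 + 11 = 131 h, about 5.5 days. No contact is scheduled in that stretch before the SFU visit.

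**6. Size of the disagreement with SAP 3.2.2.** With the same 20:00 dose and 09:00 visit, time after the end of Day 14 is 81, 105 or 129 h for visits on Day 18, 19 or 20. That is 61%, 67% or 71% of post-dose observation. Under SAP 10.2 the SFU share is 0, 0 or 13 h (0%, 0% or 7%).

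**7. SAEs.** Collection runs 30 days past the end of study. The SFU period for SAEs therefore lasts 6 + 30 − 7 = 29 to 8 + 30 − 7 = 31 days. The period is in practice almost SAE-only.

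**8. A gap in the same rule.** A participant who stops after the Day 1 dose has no Day 6 intake. With that dose at 08:00 (assumed), 168 h later is 08:00 on Day 8. An AE starting on Day 6, on Day 7 or early on Day 8 is past Day 5, follows no Day 6 intake and is within 168 h of the last dose. SAP 10.2 gives it no period.

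**The case against.** A 7-day post-dose attribution window is a legitimate analyst's choice, and SAP 6.4.2 likewise folds follow-up into the Multiple-Dose Period for medications. The rule is tied to each participant's own last dose, which suits early withdrawals, and it keeps late SAEs out of the Multiple-dose counts. All of this stands, although the SAP gives no rationale for 168 h. It argues for keeping the window, but not for leaving post-treatment events unseparated inside it.

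Four stronger readings are tempting, and the documents do not support them.

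- A reader might infer that post-cessation events cannot be told apart at all. They can: the AE listing (SAP 10.2) gives onset date and time with relative day, and SAP 3.2.1 marks events after the last dose with a plus sign and counts days from that dose.
- A reader might infer that the secondary endpoint is biased. It is incidence of TEAEs, and the TEAE definition has no upper limit, so the total is the same under any period boundary. The genotype groups share one schedule and one rule.
- A reader might expect a misleadingly empty SFU column. SAP 3.6 specifies no such column, so where SFU-attributed events would be tabulated is simply undefined.
- A reader might scale incidence up in proportion to the longer window. The documents give no event rate, and Protocol 2.3 describes AEs as dose related and easing over the first days of dosing, so a constant rate is not a safe basis.

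Moving the boundary to Day 14 for everyone is also not the answer. It would leave about 52 h after the last dose (20:00 on Day 12 to the end of Day 14) in the Multiple-dose count, and it would count off-drug time as Multiple-dose for anyone who stops early.

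**Conclusion.** The point holds in a limited form. SAP 10.2, 3.2.2, 3.6 and 6.4.2 do not agree on where the Multiple-Dose Period ends or whether follow-up is a reporting period. Under the SAP 10.2 rule, non-serious AEs reach the SFU period only with a Day 20 visit, and then for less than a day. Roughly half of the Multiple-dose AE window is post-treatment time.

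The whole-day result in step 2 needs only the documents. The hour figures and the 46% to 52% share rest on assumed clock times, and the Day 19 result assumes a visit earlier in the day than the Day 12 evening dose. How many events would change column cannot be estimated from the documents. What is affected is the period-level TEAE summaries. Total TEAE incidence, the genotype comparison, the listings and the PK analyses are not.

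**What to change.** Amend SAP 10.2 so that the split is anchored to each participant's own last dose:

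- Count as Multiple-dose the TEAEs that start from the first Day 6 dose to the last dose.
- Show TEAEs that start after the last dose, up to 168 h or the SFU visit, as a separate post-treatment column.
- Report SAEs that start later than that separately.
- State where AEs starting after Day 5 go for a participant with no Day 6 intake.
- Reconcile the wording of SAP 3.2.2, 3.6 and 6.4.2 with this rule.

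The cost is one rewritten sentence, consistent wording in the other sections, and one more table column. No new data are needed, because onset times are already recorded. The Multiple-dose percentages may fall, because post-treatment events leave that column.
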